ARGX-113-2211 is a long-term, single-arm, open-label, multicenter extension study of the pSS-qualifying efgartigimod studies designed to evaluate the long-term safety of efgartigimod in adult patients with pSS. Participants will be enrolled from both active and placebo arms of qualifying efgartigimod studies and receive efgartigimod 10 mg/kg over 48 weeks in the extension study without knowledge of their treatment assignment in the qualifying study. Eligible participants must have completed the treatment period of the qualifying study and must not have permanently discontinued the IMP in that study.

Brief Summary:

Participants will receive efgartigimod 10 mg/kg by IV infusion either Q2W or QW. The dosing regimen is based on whether the participant is a responder or nonresponder. Responder status will be determined by clinESSDAI assessments conducted on day 1, week 16, and week 24 and using the baseline of the qualifying study. Participants who are not responders at week 24 will be evaluated by PI for therapeutic failure. If a participant is a therapeutic failure, they will discontinue study treatment. If a participant is not a therapeutic failure, they will continue QW dosing regimen, and a clinESSDAI will be conducted at weeks 32, 36, 40, and 44 until confirming responder status and switching to Q2W dosing regimen. The PI will continue to evaluate the participant for therapeutic failure.

The study's primary objective is to assess the long-term safety of efgartigimod in participants with pSS. Additional assessments will be conducted, and blood samples collected to assess the effectiveness of efgartigimod at treating pSS, the PD effect of efgartigimod, and the immunogenicity of efgartigimod. Blood samples will also be collected to monitor the concentration of efgartigimod in blood over time.

Number of Participants:

Up to approximately 30 subjects who have completed the efgartigimod pSS study (ARGX-113-2106) will be enrolled for in the OLE study (ARGX-113-2211).

Note: *Enrolled* means the participant agrees to participate in the clinical study by completing the informed consent process.

[figure not shown]
Study Arms and Duration:

Each participant will participate in the following study periods:

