1.2. Schema

Abbreviations: D = day; IV = intravenous; QW = once weekly; Q2W = every 2 weeks; Wk = week.

^a QW or Q2W dosing regimen depending on responder status. Responders (defined as participants with a decrease in clinESSDAI of ≥ 3 points from baseline of qualifying study or who have a change clinESSDAI score that reclassifies their disease from moderate severity to mild severity) will be switched from QW to Q2W dosing regimen. Nonresponders will remain on QW dosing regimen. Switch points (ie, timepoints where clinESSDAI are conducted to determine responder status) will occur on day 1, week 16, and week 24. If a participant is not a responder at week 24, they will be evaluated by the PI for therapeutic failure. If not considered a therapeutic failure, the participant will continue QW dosing regimen and will return at weeks 32, 36, 40 and 44 for a clinESSDAI assessment until confirming the responder status and switching to Q2W dosing regimen or PI considers the participant to be a therapeutic failure. For QW regimen, the final dose will be administered at week 47. For Q2W regimen, the final dose will be administered at week 46.

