4. STUDY DESIGN

4.1. Overall Design

Study ARGX-113-2211 is a long-term, single-arm, open-label, multicenter extension of pSS-qualifying efgartigimod studies designed to evaluate the long-term safety of efgartigimod in adult patients with pSS. Participants will be enrolled from both active and placebo arms of qualifying efgartigimod studies and receive efgartigimod IV 10 mg/kg over 48 weeks in the extension study without knowledge of their treatment assigned in the qualifying study. To be eligible to enroll in this study, participants must have completed the treatment period of the qualifying study and must not have permanently discontinued the IMP in that study.

Participants will receive efgartigimod 10 mg/kg by IV infusion either Q2W or QW. The dosing regimen is based on whether the participant is a responder or nonresponder on day 1. Participants will be considered as responders if they have a reduction in clinESSDAI score of ≥ 3 points from baseline (ie, the final visit of a previous qualifying study) and/or a change in score that reclassifies their disease from moderate severity (clinESSDAI ≥ 5) to mild severity (clinESSDAI < 5). Participants will be considered as nonresponders if they do not have a reduction in clinESSDAI score of ≥ 3 points from baseline and/or did not reach a clinESSDAI < 5 . ClinESSDAI assessments to determine responder status using the baseline will be conducted on day 1 and weeks 16 and 24. Responders will receive IV infusions Q2W. Nonresponders will receive an infusion QW until such time that they are considered to be responders. If a participant is not a responder at week 24, they will be evaluated by the PI for therapeutic failure:

- Therapeutic failure - the participant will discontinue study treatment
- Not a therapeutic failure - the participant will continue QW dosing regimen. ClinESSDAI will be conducted at weeks 32, 36, 40, and 44 until confirming responder status and switching to Q2W dosing regimen. The PI will continue to evaluate the participant for therapeutic failure

If the participant and/or investigator consider there to be a reduction in therapeutic effect once the patient has switched to Q2W, the participant will return for an unscheduled visit during which a clinESSDAI, a blood sampling for PK and ADA will be collected.

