7. STATISTICAL CONSIDERATIONS

7.1. Missing Data

For imputation of missing values related to efficacy and safety, see appropriate section of the applicable endpoints. Missing efgartigimod concentrations will not be imputed.

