For the reporting of descriptive statistics for PK data, the mean and SD will be presented to one digit more precision than the source data except values ≥ 1000 which will be presented without the decimals and rounded to the nearest integer. The minimum, median, and maximum will be presented to the same precision as the source data. Coefficient of variation will always be reported to 1 decimal place. Individual serum concentrations will be reported as received by the bioanalytical laboratory.

Descriptive statistics for immunogenicity titer values will include the number of observed values, arithmetic mean, SE, 90% CI, median, Q1, Q3, minimum, maximum, the geometric mean, and geometric CV%.

For event-type safety data, the number and percentage of participants with an event will be shown. The denominator will be all participants in the analysis set.

For frequency tabulations and cross-tabulations, the denominator will be the number of participants. For tables where results are shown by analysis visit, the denominator will be the number of participants and analysis visit.

Missing values will not be included in the denominator count when computing percentages. For cross-tabulation of post-baseline results versus baseline results, a “missing” category will be shown for baseline results, if applicable. Percentages will be presented with 1 decimal place.

Summaries will be provided both for the overall study population as well as grouped according to treatment received in the parent study AGRX-113-2106 (efgartigimod or placebo). [Appendix 1](#) shows conventions for presentation of data in outputs.

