8.1. Disposition

The number of participants will be summarized for FAS. The number of participants per country and site will also be provided using the FAS. The number of participants who completed or discontinued the treatment and/or the study along with the reason for discontinuation will be summarized using the FAS.

Participant disposition and withdrawals will be presented for the FAS.

The enrollment failures will be summarized using number of participants who signed the informed consent form.

Copyright © 2009, 2010, 2012, 2016, 2018, 2019, 2021, 2024 IQVIA. All rights reserved. The contents of this document are confidential and proprietary to IQVIA Holdings Inc. and its subsidiaries. Unauthorized use, disclosure or reproduction is strictly prohibited.

Data will be tabulated at least for:

- Number of participants in each analysis sets.
- number and percentage of participants enrolled, completed, or discontinued the study.
- number and percentage of participants for each study discontinuation reason.
- number and percentage of participants discontinuing treatment but continuing study assessments.

A listing of participant disposition will be prepared to present information about treatment discontinuation and study discontinuation.

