13. EFFICACY OUTCOMES

13.1. Efficacy Endpoints

The efficacy analyses will be performed for the FAS and will be analyzed on data observed.

Copyright © 2009, 2010, 2012, 2016, 2018, 2019, 2021, 2024 IQVIA. All rights reserved. The contents of this document are confidential and proprietary to IQVIA Holdings Inc. and its subsidiaries. Unauthorized use, disclosure or reproduction is strictly prohibited.

13.1.1. Proportion of CRESS Responders on ≥ 3 of 5 items at Week 24 and 48

The CRESS composite measures below mentioned assessments which are developed to assess treatment efficacy in participants with pSS:

- 1) Systemic disease activity: clinESSDAI
- 2) Patient-reported symptoms: ESSPRI
- 3) Tear gland function: Schirmer’s test and OSS.
- 4) Salivary gland function: UWSF rate and SGUS
- 5) Serology (serum IgG and/or RF)

The efficacy endpoint is the proportion of responders on ≥ 3 non-missing of 5 items at week 24 and 48 using CRESS.

CRESS consists of the following items, with definitions of treatment response and lower disease activity:

1) Systemic disease activity: This will be measured with clinESSDAI (Seror [a], et al., 2016)⁸.

The clinESSDAI consists of 11 domains, related to organ involvement (cutaneous, pulmonary, renal, articular, muscular, peripheral nervous system, central nervous system, hematological, glandular, constitutional, and lymphadenopathic). The ClinESSDAI includes all ESSDAI domains except the biological domain.

Table E: Domain Weights of ClinESSDAI

Domain (activity level)	ClinESSDAI Weights
Constitutional (0-2)	4
Lymphadenopathy (0-3)	4
Glandular (0-2)	2
Articular (0-3)	3
Cutaneous (0-3)	3
Pulmonary (0-3)	6
Renal (0-3)	6
Muscular (0-3)	7
Peripheral nervous system (0-3)	5
Central nervous system (0-3) ^{Seror 2015}	5
Hematological (0-3)	2
Biological (0-2)	NA*

Copyright © 2009, 2010, 2012, 2016, 2018, 2019, 2021, 2024 IQVIA. All rights reserved. The contents of this document are confidential and proprietary to IQVIA Holdings Inc. and its subsidiaries. Unauthorized use, disclosure or reproduction is strictly prohibited.

Domain (activity level)	ClinESSDAI Weights
Score total	0-135

*NA: Not Applicable

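### Week 24 and week 48 responder proportions rest on different groups, because participants stopped as therapeutic failures leave the week 48 denominator; separately, the passages on week 36 clinESSDAI conflict

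*SAP*

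**What the plan says.** **Denominator.** SAP 13.1 fixes the basis for the efficacy endpoints: "The efficacy analyses will be performed for the FAS and will be analyzed on data observed". SAP 7.2 adds: "Missing values will not be included in the denominator count when computing percentages". On missing data, SAP 7.1 only refers onward: "For imputation of missing values related to efficacy and safety, see appropriate section of the applicable endpoints". The readable endpoint sections, 13.1.1 to 13.1.6, give no rule for a participant who has stopped treatment. CRESS is defined on at least 3 non-missing items, which does not say how to count someone with no week 48 data.

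**Stopping at week 24.** Protocol 4.1 has week 24 nonresponders evaluated by the PI, and those judged therapeutic failures stop treatment. Protocol 7.1.1 then provides an early discontinuation visit (EDV) and a safety follow-up visit (SFV).

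**What is reported about discontinuation.** SAP 8.1 says that treatment and study discontinuation "along with the reason for discontinuation will be summarized using the FAS". It also tabulates the "number and percentage of participants discontinuing treatment but continuing study assessments".

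**Responder baseline.** The Protocol 1.1 Brief Summary judges response at day 1, week 16 and "week 24 and using the baseline of the qualifying study". The schema footnote in Protocol 1.2 also counts "points from baseline of qualifying study". Protocol 4.1 measures the fall "from baseline (ie, the final visit of a previous qualifying study").

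**Week 36.** Footnote k of the Schedule of Activities (SoA, Protocol 1.3) and the note under SAP Table C (6.3) restrict week 36 clinESSDAI to week 24 nonresponders who are not failures. SAP 13.1.5 and 13.1.6 list week 36 beside weeks 16, 24 and 48 for clinESSDAI, ESSDAI and STAR, without that restriction.

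**The concern.** Durability of CRESS response is a stated secondary objective, and the plan addresses it by giving responder proportions at weeks 24 and 48. Between those visits the protocol removes participants because of a poor clinESSDAI result. This is not ordinary dropout: an outcome measured at week 24 decides who can be observed at week 48. A change between the two percentages therefore mixes any real change in response with a change in who is counted.

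The study tests no hypothesis, so no error rate is at stake. What is at stake is how the durability figures are read. The same applies to week 36: if the restriction holds, a nonresponder subset sits in the same tables and on the same plotted line as visits that cover everyone.

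**Working it through.** The plan has no response rate, failure rate or sample-size calculation to reproduce. The counts below are assumptions, with N = 30 from Protocol 9.5.

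**Step 1. Can a week 24 failure have week 48 data?**
- The SoA puts week 23 on day 162 and week 24 on day 169, with a visit window of ±2 days. Protocol 7.1.1 puts the SFV at 56 ± 3 days after the last dose.
- Earliest SFV: 162 − 2 + 53 = day 213. Latest SFV: 169 + 2 + 59 = day 230.
- SAP Table C opens the week 48 clinESSDAI window on day 324. Gap: 324 − 230 = 94 days.
- The SoA marks no clinESSDAI, ESSDAI or ESSPRI at either visit. The EDV has the tear and salivary tests (2 of the 5 CRESS items), and the SFV has IgG and RF.
- Failures declared later, at weeks 32 to 44, can have an SFV after day 324, but clinESSDAI, ESSDAI and ESSPRI are still not scheduled there.

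**Step 2. Formula.** Let x be the week 24 responders on an endpoint, d the number stopped as failures, and q the share of those failures who were responders on that endpoint. With no other change in status:

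observed week 48 proportion = (x − qd)/(N − d)

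Setting this equal to x/N gives q = x/N. Below that value the observed proportion rises, and above it the proportion falls.

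**Step 3. clinESSDAI below 5.** Assume that everyone entered the qualifying study at 5 or more and that response is judged against that study's baseline. Anyone below 5 at week 24 has then moved from moderate to mild and is a responder. A failure must still be at 5 or more, so q = 0.

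| Week 24 | d = 3 | d = 6 | d = 9 |
|---|---|---|---|
| 10/30 = 33.3% | 10/27 = 37.0% | 10/24 = 41.7% | 10/21 = 47.6% |
| 15/30 = 50.0% | 15/27 = 55.6% | 15/24 = 62.5% | 15/21 = 71.4% |
| 20/30 = 66.7% | 20/27 = 74.1% | 20/24 = 83.3% | 20/21 = 95.2% |

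Exact 90% CIs for the middle row are 33.9–66.1 at week 24, then 38.2–72.0, 43.7–78.8 and 51.3–86.8. With d = 0 nothing moves. On the fixed denominator of 30, each row keeps its week 24 value.

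**Step 4. Other endpoints, x = 15.** A clinESSDAI failure may respond on ESSPRI, CRESS or STAR. The change-based measures also use the OLE baseline (Protocol 9.3.1 and 9.3.3, SAP 6.2), which differs from the qualifying-study baseline, so q is unknown.
- q = 1/3: 14/27 = 51.9%, 13/24 = 54.2%, 12/21 = 57.1%.
- q = 1/2: no shift; for example, with d = 6, 12/24 = 50.0%.
- q = 2/3: 13/27 = 48.1%, 11/24 = 45.8%, 9/21 = 42.9%.

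**Step 5. Masking, q = 0.** Take 18/30 = 60.0% (43.4–75.0) at week 24, 6 failures, and 3 responders who lose response. Observed-case gives 15/24 = 62.5% (43.7–78.8). The fixed denominator gives 15/30 = 50.0% (33.9–66.1).

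**Step 6. Week 36, side by side.**
- Restricted: SoA footnote k and the SAP Table C note, for clinESSDAI.
- Not restricted: the SoA row for ESSDAI, and SAP 13.1.5 and 13.1.6 for clinESSDAI, ESSDAI and STAR. SAP Table D (section 11) also allows participants who start on Q2W to be found nonresponders at weeks 32 to 44.
- Linking them: ESSDAI shares its 11 clinical domains with clinESSDAI, STAR needs clinESSDAI, and Protocol 8.2.3 has sites report only clinESSDAI.

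These passages do not settle who is assessed at week 36.

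**The case against.** The strongest reply is that the loss will be visible. Protocol 9.3.1 gives sample size with frequencies and percentages, SAP 7.2 uses by-visit denominators, and SAP 8.1 tabulates discontinuations with reasons. A reader will see the number fall and can see why. That stands, so one cannot say that the selection is hidden. What remains is that no planned readable table gives the proportion on a common denominator.

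A second reply is that no estimand is defined and the study is descriptive, so counting failures as nonresponders is one choice among several. That also stands, and it is why the added table should support the observed-case result and not replace it.

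A third is that SAP 8.1 foresees participants who continue assessments off treatment. Neither document schedules week 48 efficacy visits for them, so this helps only if such visits are held outside the stated schedule. Sections 13.2 and 13.3 are redacted, but the affected secondary endpoints are in the readable 13.1. The only readable efficacy window is the one for clinESSDAI; for ESSDAI and ESSPRI the argument rests on their absence from the EDV and SFV.

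On week 36, the domains may be collected from everyone for ESSDAI, with footnote k governing only the dosing assessment. That is possible, and it is a reason to ask for reconciliation and not to assume a subset.

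**Conclusion.** The point holds. Week 24 failures count at week 24 and leave week 48 by design, so the two proportions cover different groups. In the assumed example with q = 0, 50% becomes 56%, 63% or 71% with 3, 6 or 9 failures and no change in anyone's status; with none there is no shift.

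Three stronger readings are tempting, and the documents do not support them:
- **That every week 48 proportion is inflated.** The upward direction follows only for clinESSDAI below 5, and only if participants entered the qualifying study at 5 or more (the documents do not give the entry range) and response is judged against that study's baseline. Under the Protocol 4.1 baseline, a participant at 4 at both OLE entry and week 24 could be a nonresponder while below 5. For the other endpoints, CRESS included, direction and size are unknown.
- **That every week 24 nonresponder stops, driving the proportion to 100%.** The Definitions of Terms in both documents read that way, but Protocol 4.1 leaves the decision to the PI. The passages must be reconciled.
- **That week 36 data definitely come from nonresponders only.** The passages conflict, and no size or direction is claimed.

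This is a cheap improvement to how the results can be interpreted, not a fault in a test.

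**What to change.** 1. **SAP 13.1.** Keep the observed-case proportions. Add one supportive table of the CRESS, ESSDAI, clinESSDAI, ESSPRI and STAR proportions at both week 24 and week 48 on one fixed denominator: treated participants (the SAF). The FAS is unsuitable because it holds all enrolled participants, enrolled means consented, and Protocol 5.4 includes consented participants who fail eligibility before dosing. At week 48, count participants whose recorded reason for stopping IMP is therapeutic failure, at week 24 or later, as nonresponders. Show those missing for other reasons in separate rows by reason.
2. **Make the group identifiable.** Reconcile the Definitions of Terms with Protocol 4.1 on therapeutic failure, and Protocol 1.1 and 1.2 with 4.1 on the responder baseline. Protocol 7.1.1 has the primary reason documented but does not list therapeutic failure by name, so confirm that the eCRF captures it.
3. **Week 36.** Reconcile footnote k, the Table C note, the ESSDAI row of the SoA and SAP 13.1.5 and 13.1.6. If the restriction applies to data collection, label week 36 clinESSDAI and STAR as the nonresponder subset and keep them out of the overall summaries and plots; treat ESSDAI the same way only if its domains are not collected for everyone. If the domains are collected for everyone, correct footnote k and the Table C note.

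The cost is SAP wording, one table and a clarification. The downside is that the added table is conservative where a failure may still respond: with x = 15, d = 6 and q = 1/3 it gives 13/30 = 43.3% although no status changed. That is why observed-case stays beside it.

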3. OBJECTIVES, ENDPOINTS, AND ESTIMANDS

Table 2: Study ARGX-113-2211 Objectives and Endpoints

Objectives	Endpoints
Primary	

 To evaluate the long-term safety of efgartigimod in patients with pSS 	
 Incidence and severity of AEs and AESIs, incidence SAEs, changes in laboratory test results, vital signs, and ECG results
Secondary	

 To evaluate effect and assess long-term data on durability of CRESS response 	
 Proportion of CRESS responders on ≥ 3 of 5 items at weeks 24 and 48 (refer to Section 8.2.1). The 5 items are: 
 Systemic disease activity: clinESSDAI Patient-reported symptoms: ESSPRI Tear gland function: Schirmer’s test and OSS Salivary gland function: UWSF rate and SGUS Serology: serum IgG and/or RF

 To evaluate the effect of efgartigimod on clinical efficacy parameters 	
 Proportion of participants with minimal clinically important improvement from baseline in ESSDAI: improvement of ≥ 3 points in ESSDAI score at weeks 24 and 48 Proportion of participants with low disease activity: ESSDAI score of < 5 at weeks 24 and 48 Proportion of participants with minimal clinically important improvement from baseline in clinESSDAI: improvement of ≥ 3 points in clinESSDAI score at weeks 24 and 48 Proportion of participants with low disease activity: clinESSDAI score of < 5 at weeks 24 and 48 Proportion of participants with minimal clinically important improvement from baseline in ESSPRI: decrease of ≥ 1 point or $\geq 15\%$ at weeks 24 and 48 Change from baseline in ESSDAI score at weeks 24 and 48 Change from baseline in clinESSDAI score at weeks 24 and 48 Change from baseline in ESSPRI score at weeks 24 and 48

 To evaluate the effect of efgartigimod on STAR 	
 Proportion of STAR responders (score of ≥ 5) at weeks 24 and 48 when compared to baseline

Objectives	Endpoints

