9.3.3. Secondary Endpoint(s) Analysis

The key secondary endpoints of CRESS, ESSDAI, clinESSDAI, ESSPRI, and STAR responders will be assessed at week 24 and week 48.

The proportion along with an exact 90% CI of CRESS, ESSDAI, clinESSDAI, ESSPRI, and STAR responders will be presented at week 24 and week 48.

[figure not shown]
Secondary endpoints of change from OLE baseline in ESSDAI, clinESSDAI, and ESSPRI scores will be summarized descriptively at week 24 and week 48. Observed data will also be summarized at OLE baseline, week 24 and week 48.

Plots of mean changes from the OLE baseline will be presented along with their 90% confidence intervals at each scheduled timepoint for ESSDAI, clinESSDAI, and ESSPRI. Box and Whisker plots will also be presented for the change from OLE baseline for each scheduled timepoint.

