2. STUDY OBJECTIVES AND ESTIMANDS

[figure not shown]
Table A : Objectives and Endpoints

Objectives	Endpoints
Primary	

 To evaluate the long-term safety of efgartigimod in patients with pSS 	
 Incidence and severity of adverse event (AEs) and adverse events of Special interest (AESIs), incidence serious adverse events (SAEs), changes in laboratory test results, vital signs, and electrocardiogram (ECG) results
Secondary	

 To evaluate effect and assess long-term effect of efgartigimod on durability of CRESS response 	
 Proportion of Composite of Relevant Endpoints for Sjögren’s Syndrome (CRESS) responders on ≥ 3 of 5 items at weeks 24 and 48 (refer to Section 8.2.1 of the protocol). The 5 items are: 
 Systemic disease activity: clinical EULAR Sjögren’s syndrome disease activity index (clinESSDAI) Patient-reported symptoms: EULAR Sjögren’s Syndrome Patient Reported Index (ESSPRI) Tear gland function: Schirmer’s test and ocular staining score (OSS) Salivary gland function: unstimulated whole salivary flow (UWSF) rate and salivary gland ultrasonography (SGUS) Serology: serum - immunoglobulin G (IgG) and/or rheumatoid factor (RF)

Copyright © 2009, 2010, 2012, 2016, 2018, 2019, 2021, 2024 IQVIA. All rights reserved. The contents of this document are confidential and proprietary to IQVIA Holdings Inc. and its subsidiaries. Unauthorized use, disclosure or reproduction is strictly prohibited.

Objectives	Endpoints

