3.2. Sample Size

No formal sample size calculation has been planned for this phase 2 open-label extension (OLE) study. Up to approximately 30 subjects who have completed the efgartigimod pSS studies will be enrolled for the OLE study.

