6.6. Statistical Tests

The default significant level will be (10%); confidence intervals (CIs) will be 90% and all tests will be two-sided, unless otherwise specified in the description of the analyses.

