presence of hypoechoic areas in parenchyma, graded 0–3	presence of hypoechoic areas in parenchyma, graded 0–3	presence of hypoechoic areas in parenchyma, graded 0–3	presence of hypoechoic areas in parenchyma, graded 0–3
presence of hyperechoic foci, graded 0–3 in parotid glands	presence of hyperechoic foci, graded 0–3 in parotid glands	presence of hyperechoic foci, graded 0–1 in submandibular glands	presence of hyperechoic foci, graded 0–1 in submandibular glands

Copyright © 2009, 2010, 2012, 2016, 2018, 2019, 2021, 2024 IQVIA. All rights reserved. The contents of this document are confidential and proprietary to IQVIA Holdings Inc. and its subsidiaries. Unauthorized use, disclosure or reproduction is strictly prohibited.

clearness of the salivary gland border, graded 0–3	clearness of the salivary gland border, graded 0–3	clearness of the salivary gland border, graded 0–3	clearness of the salivary gland border, graded 0–3
Score Range – 0 to 13	Score Range – 0 to 13	Score Range – 0 to 11	Score Range – 0 to 11

The overall ultrasound score is calculated by summation of the grades for the 5 above mentioned parameters - for all 4 major salivary glands. The overall ultrasound score can range from 0 to 48.

If any parameter is not assessed, the whole score cannot be derived, no substitutes for missing data.

Responder for salivary gland function has two components:

- UWSF: at least 25% increase in score, or if score is 0 mL/min at baseline, any increase from baseline OR
- SGUS: at least 25% decrease in total Hocevar score³ from baseline

Unstimulated whole salivary flow (UWSF) will be measured as ml per minute.

5) Serology: It is measured with serum IgG and RF

For the biological domain, levels of rheumatoid factor (RF), and IgG are measured based on blood sample examined in the laboratory. The amount of RF antibody will be measured in - (IU/ml) [(IU/ml)] and IgG will be assessed in (g/L).

A responder for biological domain is defined as follows:

- A response is defined as $\geq 10\%$ reduction in IgG from baseline or
- A response is defined as $\geq 25\%$ decrease in rheumatoid factor (RF) from baseline.

The proportion of participants with CRESS responders on ≥ 3 of 5 items at week 24 and 48 will be provided along with exact 90% CIs.

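### Durability of CRESS response is the first secondary objective, but the readable plan reports only separate week-24 and week-48 proportions, which do not identify how many responders keep their response

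*SAP*

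**What the plan says.** Protocol Section 3 (Table 2) lists as the first secondary objective: "To evaluate effect and assess long-term data on durability of CRESS response". SAP Section 2 has it as: "To evaluate effect and assess long-term effect of efgartigimod on durability of CRESS response". The only endpoint beside it in either document is the proportion of participants responding on at least three of the five CRESS items at weeks 24 and 48.

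The analysis follows that endpoint. Protocol 9.3.3 states that proportions with exact 90% intervals for "CRESS, ESSDAI, clinESSDAI, ESSPRI, and STAR responders will be presented at week 24 and week 48". SAP 13.1.1 repeats this for CRESS: "The proportion of participants with CRESS responders on ≥ 3 of 5 items at week 24 and 48 will be provided along with exact 90%" confidence intervals. SAP 6.6 sets the level: "confidence intervals (CIs) will be 90% and all tests will be two-sided".

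SAP 13.1 bases efficacy analyses on observed data in the full analysis set, and SAP 7.2 leaves missing values out of percentage denominators. The week-24 and week-48 proportions can therefore describe different sets of participants. The readable text defines no sustained CRESS response, no week-48 status among week-24 responders, no time to loss of CRESS response and no cross-tabulation of the two visits.

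**The concern.** Durability, in its usual sense, belongs to the participant: does someone who responds at one visit still respond later? Two group proportions do not answer that, because participants who lose response can be offset by others who gain it.

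Such offsetting is plausible here. Under Protocol 4.1, clinESSDAI responders receive the Q2W regimen and continuing clinESSDAI nonresponders stay on QW, so changes in both directions can occur between the two visits. Protocol 4.3 gives maintenance of efficacy under less frequent dosing as the reason for studying Q2W, which is also a question about the same people over time.

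What is at stake is the reading of the first secondary result. Similar proportions at weeks 24 and 48 invite the conclusion that response lasted, and the planned output would look the same whether or not it did.

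**Working it through.** **Inputs.** The documents state no expected CRESS rate, power or effect size, so there is no planned figure to reproduce. SAP 3.2 gives only a ceiling: "Up to approximately 30 subjects who have completed the efgartigimod pSS studies will be enrolled for the OLE study". I take n = 30 and, as an assumption, responder counts from 9/30 to 27/30. Intervals are exact, 90%, two-sided, as planned.

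**Bounds on retention.** Let a participants respond at week 24 and b at week 48, with the same n seen at both visits. The number who respond at both lies between max(0, a + b − n) and min(a, b). Dividing by a gives the range of retention.

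| Week 24 | Week 48 | Retained | Retention |
|---|---|---|---|
| 9/30 | 9/30 | 0 to 9 of 9 | 0% to 100% |
| 15/30 | 15/30 | 0 to 15 of 15 | 0% to 100% |
| 18/30 | 18/30 | 6 to 18 of 18 | 33.3% to 100% |
| 20/30 | 20/30 | 10 to 20 of 20 | 50.0% to 100% |
| 24/30 | 24/30 | 18 to 24 of 24 | 75.0% to 100% |
| 27/30 | 27/30 | 24 to 27 of 27 | 88.9% to 100% |
| 15/30 | 12/30 | 0 to 12 of 15 | 0% to 80.0% |
| 21/30 | 15/30 | 6 to 15 of 21 | 28.6% to 71.4% |

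The lower bound is 0% only when a + b ≤ n. The upper bound is 100% only when b ≥ a. The full range needs both conditions.

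**What the planned output shows.** With 15/30 at each visit the report gives 50% (exact 90% CI 33.9% to 66.1%) twice. That output is the same if retention is 0/15 (0% to 18.1%) or 15/15 (81.9% to 100%).

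**Observed-case denominators.** Suppose 15/30 respond at week 24, six nonresponders then leave, 12 of the 15 responders still respond at week 48 and nobody else gains response. The report reads 12/24 = 50.0%, an apparent lack of change. Retention is 12/15 = 80%, and 12/30 = 40.0% of those enrolled respond. Given only that the six who left were nonresponders, nine week-24 nonresponders remain, so the same 12/24 is compatible with retention from (12 − 9)/15 = 20% to 12/15 = 80%.

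**Other planned outputs.** The Kaplan-Meier analysis in Protocol 9.3.4 follows reversion to the QW regimen. The regimen subgroups in SAP 13.1.5 cover clinESSDAI and ESSDAI scores. Neither uses CRESS status.

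**The case against.** The strongest reply is that the SAP implements the protocol endpoint exactly as written, in a descriptive study with no hypothesis and no estimand. The objective also asks for the effect itself, which the proportions serve directly, and a stable group rate is one descriptive reading of durability. With about 30 participants, listings with derived variables would let a reader count retention by hand. A retention proportion would be imprecise. With no comparator, and with a group selected on a thresholded composite, some apparent loss would be regression to the mean.

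Most of this stands as a limit on how much weight the point carries. It does not remove the gap: a hand count from listings is not a planned summary, and imprecision is a reason to show the interval.

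A reader might infer several stronger things that the documents do not support:

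- That the two proportions always leave retention anywhere from none to full. At high rates they bound it quite tightly: 24/30 twice forces at least 75% if all 30 are seen at both visits.
- That the design makes one-for-one replacement likely. Dosing follows clinESSDAI response, not CRESS, so a CRESS responder may be on QW and a CRESS nonresponder on Q2W. Participants who worsen on Q2W can return to QW, and therapeutic failures stop treatment.
- That loss of effect after less frequent dosing would be fully hidden. The regimen-subgroup summaries, the Kaplan-Meier analysis, the regimen counts by visit and the unscheduled clinESSDAI assessments all bear on it, though not through CRESS.
- That no linked CRESS analysis exists anywhere. SAP 13.2 and 13.3 are redacted and Protocol 9.3.4 has a redacted item. The readable exploratory endpoints list none.

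**Conclusion.** The point holds as a mismatch between objective and endpoint. In the readable text, the only planned CRESS responder summaries over time are separate observed-case proportions at weeks 24 and 48, and these do not identify within-participant retention. How much they leave open depends on the rates. With the same 30 participants at both visits, it is everything from 0% to 100% when the rates sum to at most 100% with no fall at week 48, and a narrower range otherwise. The documents give no expected rate, so which case applies cannot be settled in advance.

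This is not an error in an inferential result, since none is planned. It is a cheap improvement that should be made, because without it the durability part of the first secondary objective has no summary that addresses it directly. It concerns weeks 24 to 48 of the extension only. Under SAP 6.2 the change-based CRESS items are measured from the last parent-study value, so persistence of a response gained in the parent study is a separate matter.

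**What to change.** Keep both proportions and add the following to SAP 13.1.1:

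- A week 24 by week 48 cross-tabulation of CRESS responder status, with missing week-48 status as its own category and the reason shown.
- The proportion of week-24 CRESS responders who also respond at week 48, with an exact 90% interval, overall and by parent-study arm (SAP 7.2 already plans summaries by parent treatment).
- That proportion on observed data, to match the SAP rule. As a sensitivity summary, repeat it with week-24 responders who stopped treatment and have no week-48 value counted as not retained. Making that count the main analysis would depart from the observed-data rule.
- The number of new week-48 responders, reported separately.

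No extension to STAR is needed, because its objective does not mention durability.

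The cost is one table and a few sentences. The schedule of activities has all CRESS components at both visits, so no new data are required. The downside is a smaller denominator and a wide interval: 12/15 gives 56.0% to 94.3%, and the split by parent arm will be less precise still.
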